4. a. To assess if variability in physical therapy milestones post-op is associated with flare at 6 weeks
 - b. To assess if variability in physical therapy milestones post-op is associated with patient reported outcome measures at 1 year (for e.g., HAQ, DAS-28, HOOS, KOOS).
5. To evaluate if RA patients who flared within 6 weeks after arthroplasty exhibit an increase in ROCK activation at 6 weeks over and above pre-operative baseline levels, compared with patients who don't flare.
6. To better understand the molecular signature of RA flare and prodrome to RA flare. Blood samples harvested during various states of RA disease activity will be analyzed by RNA sequencing and Luminex® protein array to establish which pathways fluctuate most during disease worsening as well as prodrome to worsening. RA flare and the prodrome to flare will be measured by patient self-report using validated instruments of patient reported prodromal symptoms, patient reported disease activity measures and the OMERACT PFQs.

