- 3. RAPID 3 weekly for 6 weeks and every 3 months for 1 year after arthroplasty, DAS-28, HOOS, KOOS, shoulder/elbow survey, patient global at baseline, 6 weeks, and 1 year.
- 4. Physical therapy functional milestones (PT questionnaire) at baseline and weekly for 86 weeks.
- 5. Biological markers of immune activation including levels of IRF4, IRF5, IRF8, IBP/Def6, SWAP-70, ROCK1, ROCK2 in synovial tissue taken at surgery. Levels of the same immune biomarkers in the peripheral blood measured pre-operatively, at 6 weeks post-operatively and at one year post-operatively.
- 6. Measurement of discrete set of genes expressed in circulating monocytes in RA patients obtained at baseline and weekly for 6 weeks after surgery in a subset of patients at high risk for flare (based on patients who withdrew biologics)

[Help](#)

ID: 2014-233

View: 2.1 Background

[Help](#)

BACKGROUND - Be sure to answer each question individually

1.0 Explain why these research questions are being asked:

RA patients who undergo arthroplasty have severe erosive disease; preliminary data suggests a flare rate as high as 26% in the post-operative period. This study would confirm the rate of post-operative flare, and evaluate the clinical and biologic factors which predict flare. We would also look at the impact of flare on arthroplasty outcomes (HOOS, KOOS, elbow/shoulder survey) and RA disease status (HAQ, DAS-28, RAPID) and better understand the biology of flare.

Flare after arthroplasty is clinically relevant, as medications are typically withheld at the time of surgery with the aim of diminishing surgical site infections.

However, patients who flare may not be able to adhere to post-operative rehabilitation regimens, leading to worse functional outcomes. In addition, patients who flare may have difficulty achieving remission or low disease activity when medications are re-started, leading to worse disease outcomes. There is little information about the characteristics and outcome of flare in the post-operative period. Better understanding of the incidence and clinical characteristics of post-operative flare and the means to predict who will be most likely to flare could lead to more tailored management strategies and potentially better arthroplasty and disease outcomes.

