- If for any reason subjects are unable to provide blood at their 6-week or 1-year follow-ups (for example, if the subject was too busy, the line at phlebotomy was too long, or the subject simply did not schedule a 1-year follow-up), we will contact the subject and ask them if they would like to have the blood drawn by Apex Laboratory, Inc, a mobile laboratory capable of visiting patients to draw blood in their homes. If they express interest, we will sent them a new informed consent form, cover letter, and prepaid return envelope. When we recieve the signed consent form, we will call the subject to coordinate an Apex Laboratory visit date. Apex will call the patient to coordinate the proper time to arrive, and will draw a maximum of 1.5 tablespoons of blood for ESR and CRP blood tests. The results of these tests will be communicated to the study research assistant through Apex's HIPAA-compliant web-based platform.

Surgical sample:

- During surgery, the subjects' surgeon will take samples of the tissue removed as part of their surgery from their joint. Specifically for THR, the femoral head will be collected intra-operatively from standardized anatomic sites, (fovea and capsular reflection). For TKR, tissue samples of the patella cartilage, distal femur and proximal tibia, and synovium from the suprapatellar pouch will be collected intra-operatively.
- We collect and analyze this tissue to learn more about the cellular activity that occurs with RA flare. Tissue will be processed first in pathology: sample saved in OCT and 2 slides stained with H&E. Slides will be scored according to a modified Scanzello scoring system. Synovial tissue and PBMCs will be processed according the standard operating procedures established by the AMP network. Cellular samples will be analyzed at HSS, and shared with the AMP network for additional specialized technical analytics to explore markers and pathways expressed in tissue and cells, using (but not limited to) those being explored in the AMP network such as RNA-Seq, ATAC-Seq, CyTOF, FACS.
- We will also photograph the specimen using the Pathology Lab equipment. This photograph will be de-identified before it is used for research purposes. We will also capture de-identified microscopy images of H&E slides prepared from these samples.

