
cells will be viably frozen for future validation of RNA seq data. Plasma will be used for measurement of cytokines and other inflammatory proteins.

Tissue analysis (research assistant, surgeon): Special attention will focus on obtaining samples of tissues from standardized anatomic locations, representing entheses, joint margins and synovial lining, and synovial tissue will be collected intra-operatively from standardized anatomic sites, (fovea and capsular reflection). The tissue specimens obtained from these locations will be taken directly to the Histopathology lab and divided into three aliquots. As discussed with [name], all processing in Pathology will be performed by the study Research Assistant under the direct supervision of the study pathologist or representative.

- a. The first aliquot will be frozen and sectioned for staining with H&E for tissue identification and for any later processing that might require fresh-frozen tissue. The frozen tissue block (minimum 0.5 cm in diameter) will be preserved in the cryomold and taken to [name] lab for storage in freezer (-80°C).
- b. The second aliquot will be stored fresh in a tube with RNAlater and will be brought by a research assistant to The Rockefeller University Collaborative Research Center to be used for RNAsequencing. The sample will be frozen and subsequently thawed and RNA will be extracted using the Trizol Plus RNA purification system (Life Technologies). RNA will be reverse transcribed and a cDNA library will be generated and sequenced on a HighSeq 2500. Data will be processed by filtering, genome mapping with STAR, and raw read counts will then be processed with edgeR for differential gene expression comparing synovial samples from patients who flared to those who did not flare in 6 weeks of follow up.
- c. The third aliquot will be processed in the HSS pathology laboratory for fixation, paraffin embedding and sectioning, and standard of care H+E staining.

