In aim 5 and 6 we will compare levels of serum and tissue biomarkers between RA who flare and RA who do not flare using T-tests or chi-square tests, as appropriate. We will correlate self-report functional scores and biomarkers with the development of flare using Spearman correlations.

After sequencing, the reads will be processed by the New York Genome Center in a dedicated RNA-Seq pipeline, consisting of ribosomal RNA filtering, genome mapping with STAR, various QC metrics obtained with picard tools and transcript quantification with HTSeq-count. The raw read counts will then be processed with one of the Bioconductor package for Differential Gene expression (DESeq, edgeR, or limma/voom).

[Help](#)

ID: 2014-233

View: 2.4 Consent Information

[Help](#)

Consent Information

1.0 Describe how, when, and where the consent process will be initiated:

If possible, before coming in to the hospital (either for a pre-operative visit or their surgery), patients will be called by a research team member to discuss the study and evaluate their interest in participating. Patients who are interested will then be consented prior to surgery by the study research assistant or their treating surgeon, or rheumatologist either in the office, in pre-surgical screening, or in the pre-op holding area. If convenient, patients can additionally review the study protocol with the coordinator over the phone, but they will always be consented in person. The consent will be placed in the patients' hospital chart.

In the event that a potential participant requires a translator and is scheduled to have surgery on a weekend, a co-investigator of the research study can contact the potential participant prior to the day of their surgery and consent the patient over the phone. The Hospital for Special Surgery's Language Services Phone Interpreter or in-house employee will translate the Informed Consent to Participate in a Research Study Involving Genetic Testing, the Short Form Consent, and the Research Authorization Form. The translator would function as the witness to the consenting process. If the participant agrees to enroll, the participant will sign these forms in person on the day of their first study visit.

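### Joint tissue is sampled once, at surgery, before any post-operative flare, so it belongs under Aim 3 (predictors of flare) and not in the Aims 5 and 6 comparison

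*Combined protocol and SAP*

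**What the plan says.** - **When tissue is taken.** Section 2.6 (Surgical sample) says the "surgeon will take samples of the tissue removed as part of their surgery from their joint". Secondary outcome 5 (section 2, item 5.0) gives tissue one time point: "SWAP-70, ROCK1, ROCK2 in synovial tissue taken at surgery".
- **When blood is taken.** The same outcome gives blood three: "Levels of the same immune biomarkers in the peripheral blood measured pre-operatively, at 6 weeks post-operatively and at one year post-operatively".
- **What flare is.** Aim 1 (section 2, item 2.0) counts flare within 6 weeks after surgery, through a DAS28 increase or the patient rating their RA as worse than before the operation, together with a supporting criterion.
- **Stated purpose of the tissue.** Section 2.6: "We collect and analyze this tissue to learn more about the cellular activity that occurs with RA flare".
- **Aim 5** asks whether patients who flare "exhibit an increase in ROCK activation at 6 weeks over and above pre-operative baseline levels", compared with those who do not.
- **Aim 6** describes blood samples taken in different states of disease activity. It does not name tissue.
- **Analysis.** Section 2.11.1, item 3.0: "In aim 5 and 6 we will compare levels of serum and tissue biomarkers between RA who flare and RA who do not flare", by t-tests or chi-square tests. Section 2.7 (Tissue analysis, second aliquot) runs edgeR "comparing synovial samples from patients who flared to those who did not flare in 6 weeks of follow up".

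**The concern.** Aim 5 concerns a change between two time points. Tissue has one, and it precedes the event that defines the groups. A flare versus non-flare tissue contrast therefore estimates a difference already present at surgery. The purpose in section 2.6 and the placement under Aims 5 and 6 invite a different reading, namely activity during flare. Neither section 2.7 nor section 2.11.1 labels the contrast as a baseline or predictor comparison.

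The contrast is also open to confounding by disease activity on the day of sampling. The flare rule depends on baseline DAS28: a rise of 0.6 suffices from a baseline of 3.2 or more, against 1.2 otherwise. Hypothesis 3 expects patients who flare to have worse pre-operative disease activity. A marker that tracks inflammation at surgery could then differ by later flare status with no flare-specific biology behind it, and neither tissue analysis names baseline DAS28.

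**Working it through.** The plan gives no figure for this point, so the main check sets timing against aim.

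| Aim | What it needs | What tissue supplies |
|---|---|---|
| 3 | Baseline features, then flare within 6 weeks | One surgery-day sample before the outcome: fits |
| 5 | Level at 6 weeks compared with the pre-operative level | No 6-week sample: cannot be answered |
| 6 | Blood across disease states, flare and prodrome | Not blood, and one occasion only: mismatch |

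Every tissue sample precedes the post-operative flare, by up to 6 × 7 = 42 days. None can be taken during it. Blood is repeated and can address change.

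**Size of the groups.** Inputs are 47 evaluable RA patients and a 26% flare rate (section 2.11.1). 0.26 × 47 = 12.2, so about 12 flare and 47 - 12 = 35 non-flare. This is an upper guide for tissue, because 47 is the sample size for the primary outcome and not a tissue count. Sections 2.6 and 2.62 specify tissue sites only for hip and knee, while shoulder and elbow patients are also eligible. A two-sided 5% t-test on 12 versus 35 has 80% power for a standardised difference of about 0.96. At a 10% flare rate (5 versus 42) the figure is about 1.36.

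**Possible confounding by baseline DAS28.** The documents give no inputs for this, so all of the following are assumptions:
- baseline DAS28 with mean 3.2, 3.8 or 4.4 and SD 1.2;
- DAS28 change with mean 0 and SD 0.9;
- flare by the DAS28 limb alone (0.6/1.2 rule);
- a tissue marker correlated 0.3, 0.5 or 0.7 with baseline DAS28 and unrelated to flare otherwise.

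The simulation used 1,000,000 patients per scenario:

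| Baseline-change correlation | Flare minus non-flare tissue difference (SD) |
|---|---|
| 0 | about 0.07 to 0.32 |
| -0.2 | about -0.05 to 0.08 |
| -0.33 | about -0.19 to -0.04 |
| -0.5 | about -0.39 to -0.14 |

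With zero correlation the simulated flare rate is 17% to 23%. A linear baseline DAS28 term brings the difference to 0.00 in every scenario. That is expected here, because the simulated marker relates to flare only through baseline DAS28, and linearly.

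**The case against.** The strongest reply is that the investigators already intend a predictor reading. Section 2.1 (Background) speaks of precursors of flare from blood and tissue obtained at arthroplasty, of candidate predictors for further study, and of tissue and serum biomarkers associated with flare, with validation left to a larger study. Secondary outcome 5 says plainly that the tissue is "in synovial tissue taken at surgery", and section 2.7 groups it by flare during follow-up, so a careful reader can see that sampling comes first. All secondary outcomes are called exploratory. This stands, and it limits the point to a mismatch between aim and sample.

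Several stronger readings are tempting and are not supported:
- *The investigators will report a tissue difference as the biology of active flare.* No section says so. The wording in 2.6 and 2.11.1 permits that reading, and the Background points the other way.
- *Aim 3 leaves tissue out.* Aim 3 covers biomarkers including the ROCK pathway. Tissue is not named there, but it is not excluded.
- *Tissue has no bearing on Aim 6.* Aim 6 includes the prodrome, which precedes flare. The valid point is that Aim 6 specifies blood.
- *Confounding will inflate the tissue signal.* This needs DAS28 change to be independent of baseline. A correlation of -0.33 reverses the sign in all scenarios. The simulation also omits the patient-reported limb and the supporting criterion. With 12 versus 35 patients, a difference of 0.07 to 0.32 SD would be detected only about 5% to 15% of the time.

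Adjustment for DAS28 is not neutral either. If synovial inflammation drives DAS28, the adjusted result may remove part of the signal sought. This is why the adjusted result should accompany the unadjusted one and not replace it.

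**Conclusion.** The point holds as a mismatch between aim and sample. One surgery-day tissue sample cannot answer Aim 5, and Aim 6 as worded draws on blood. Tissue can address association with later flare, which is Aim 3. This conclusion rests on the plan's own timing and needs no numerical assumption.

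The consequence is limited to the interpretation of exploratory tissue results, with about 12 expected flares if the 26% rate and 47 evaluable patients hold. The primary flare rate and the repeated blood analyses are unaffected. The case for showing a DAS28-adjusted result rests on the 0.6/1.2 rule and Hypothesis 3, and not on any particular estimate of bias. A reader might infer a known upward bias, but across the assumed baseline-change correlations from 0 to -0.5 the difference runs from about +0.32 to -0.39 SD.

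**What to change.** 1. In section 2.11.1, item 3.0, restrict the Aims 5 and 6 comparison to blood.
2. Under Aim 3, name the tissue markers and the synovial RNA sequencing contrast of section 2.7 as surgery-day predictors of flare within 6 weeks.
3. Reword the purpose in section 2.6 (Surgical sample) to say that tissue is used to learn whether features present at surgery are associated with later flare. Base statements about activity during flare on post-operative blood.
4. Report the tissue contrast twice: unadjusted, and with continuous baseline DAS28 as a covariate, including in the edgeR design. State that the adjusted result concerns association beyond baseline disease activity.

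The cost is wording in three sections and one covariate that is already collected, with no new samples, visits or patients. The adjusted model spends one degree of freedom with about 12 expected flares and answers a narrower question. Tissue findings could no longer be presented as a signature of active flare.

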2.0 Will you be collecting human fluid or tissue? ☒ Yes ☐ No

If yes, what will you be collecting? ☒ Fluid ☒ Tissue
(Intraoperative and/or outpatient collection)

[Help](#)

ID: 2014-233 View: 2.61 Fluid Specimen Collection

[Help](#)

Fluid Specimen Collection

Please choose form the following and provide requested information.

1.0 ☒ Blood/serum/plasma

Volume:

59 mL (3.99 tablespoons) first visit, 36.5 mL (2.47 tablespoons) for follow-up visits

Timing and Frequency of collection:

During the surgery

Storage requirements:

Purpose:

☐ Within SOC

Describe testing and who will do testing:

☒ Additional collection for research purposes

Describe testing and who will do testing:

☐ Urine

Volume:

Timing and Frequency of collection:

Purpose:

☐ Within SOC

Describe testing and who will do testing:

☐ Additional collection for research purposes

Describe testing and who will do testing:

☐ Saliva

Timing and Frequency of collection:

Purpose:

☐ Within SOC

Describe testing and who will do testing:

☐ Additional collection for research purposes

Describe testing and who will do testing:

☐ Synovial Fluid

Volume:

Timing and Frequency of collection:

Site:

Surgical Field: ☐ or **Aspiration:** ☐

Purpose:

☐ Within SOC

Describe testing and who will do testing:

☐ Additional collection for research purposes

Describe testing and who will do testing:

[Help](#)

ID: 2014-233

View: 2.61 Fluid Specimen Collection - continued

[Help](#)

Fluid Specimen Collection - continued

Please choose from the following and provide requested information.

☐ Other (e.g. cerebral spinal fluid, cheek cells, bronchial lavage, stool, etc)

Describe specimen:

Volume:

Timing and Frequency of collection:

Purpose:

☐ Within SOC

Describe testing and who will do testing:

☐ Additional collection for research purposes

Describe testing and who will do testing:

1.0 Will specimens be sent to an individual or institution outside of HSS? (i.e. external Central Laboratory) ☐ Yes ☐ No

If yes, where/to whom and what testing will be done:

2.0 Is fluid being collected for genetic testing? ☒ Yes ☐ No

If yes, describe testing:

3.0 Is fluid being stored for future testing? ☒ Yes ☐ No

If yes, describe testing:

The samples may be used for testing even after this study has been completed. Further research tests may help us learn more about the disease and response to drugs or treatment. However, future testing on the patient's biological samples may be used for any type of biomedical research, which may or may not be related to the purpose of this study. The results of these future tests will not be shared with the patient.

[Help](#)

ID: 2014-233

View: 2.62 Tissue Specimens Collection

[Help](#)

Tissue Specimens Collection

1.0 Status of Tissue

☐ FRESH

Will frozen tissue be needed? ☐ Yes ☐ No

How will it be delivered to Histopathology? Name/Extension/Beeper #.

☐ FIXED/PARAFFIN EMBEDDED

2.0 ☒ Bone

Site (Specific joint/area):

Femoral head, distal femur, proximal tibia

Purpose:

☐ Within SOC

Describe testing and who will do testing:

☒ Additional collection for research purposes

Describe testing and who will do testing:

Specifically for THR, the femoral head will be collected intra-operatively from standardized anatomic sites, (fovea and capsular reflection). For TKR, tissue samples of the patella cartilage, distal femur and proximal tibia, and synovium from the suprapatellar pouch will be collected intra-operatively.

☐ Bone Marrow

Method of collection: ☐ Biopsy ☐ Aspirate

Site (Specific joint/area):

Purpose:

☐ Within SOC

Describe testing and who will do testing:

☐ **Additional collection for research purposes**

Describe testing and who will do testing:

☒ **Cartilage**

Site (Specific joint/area):

Patellar cartilage

Purpose:

☐ **Within SOC**

Describe testing and who will do testing:

☒ **Additional collection for research purposes**

Describe testing and who will do testing:

☐ **Meniscus**

Site:

Purpose:

☐ **Within SOC**

Describe testing and who will do testing:

☐ **Additional collection for research purposes**

Describe testing and who will do testing:

[Help](#)

ID: 2014-233

View: 2.62 Tissue Specimens Collection - continued

[Help](#)

Tissue Specimens Collection - continued

☐ **Retrieved Device for Biomechanical Testing**

Site:

☒ **Synovium**

Site (specific joint/area):

Synovium from the suprapatellar pouch will be collected intra-operatively.

Purpose:

☐ **Within SOC**

Describe testing and who will do testing:

☒ **Additional collection for research purposes**

Describe testing and who will do testing:

☐ **Other (i.e. punch biopsy, nucleus pulposus/annulus fibrosus, or other collected tissue/biopsies)**

Provide additional information:

Purpose:

☐ **Within SOC**

Describe testing and who will do testing:

☐ **Additional collection for research purposes**

Describe testing and who will do testing:

1.0 Will specimens be sent to an individual or institution outside

of HSS? (i.e. external Central Laboratory) ☐ Yes ☐ No

If yes, where/to whom and what testing will be done:

2.0 Is tissue being collected for genetic testing? ☐ Yes ☒ No

If yes, describe testing:

3.0 Is tissue being stored for future testing? ☐ Yes ☐ No

If yes, describe testing:

[Help](#)

ID: 2014-233

View: 2.7 Data Collection

[Help](#)

Data Collection

1.0 Indicate what data will be collected.

PARTICIPANT INTAKE

New form location
1. Interest in electronic surveys
2. Symptom onset
3. Date of diagnosis
4. Ethnicity
5. Race
6. Highest level of completed education
7. Current employment status
8. # other people at home
9. Personal income
10. Smoking history
11. Alcohol
12. Relative with RA/PsA/OA/broken hip
13. Other diseases in family

14. Rheumatologist contact info
15. Modified Charlson/SANGA comorbidity index

Day-of-surgery allowed blood draw is 58.5mL (well below the IRB cap of 550mL):

- **30mL** whole blood in green top heparin tubes (3 tubes, 10mL each, for PBMC isolation)
- **8.5mL** speckle top tube (1 tube, to be spun by research assistant and aliquotted for freezing at -80)
- **2.5mL** for PAXgene tubes (1 tube, to be frozen by the research assistant)
- If not ordered at Pre-Surgical Screening, **3mL** lavender top for erythrocyte sedimentation rate (as marker of inflammatory levels)
- If not ordered at Pre-Surgical Screening, **5mL** into gold serum separator tube for c-reactive protein levels (as marker of inflammatory levels)
- If not available in medical record, **10mL** for combined Rheumatoid Factor (RF) and Anti-Citrullinated Protein Antibody (ACPA, also known as anti-CCP)

$30 + 8.5 + 2.5 + 3 + 5 + 10 = 59 \text{ mL}$, which is 3.99 tablespoons

Follow-up visit collection is 36.5mL (well below the IRB cap of 550mL):

- **20mL** whole blood in green top heparin tube (2 tubes, 10mL each, for PBMC isolation)
- **8.5mL** speckle top tube (1 tube, to be spun by research assistant and aliquotted for freezing at -80)
- If not ordered by treating physician, **3mL** lavender top for erythrocyte sedimentation rate (as marker of inflammatory levels)
- If not ordered by treating physician, **5mL** into gold serum separator tube for c-reactive protein levels (as marker of inflammatory levels)

$20 + 8.5 + 3 + 5 = 36.5 \text{ mL}$, which is 2.47 tablespoons

